# Research Protocol

## 1. Research Background

With the continuous accumulation of medical imaging, electronic medical records (EMRs), and multimodal clinical data, how to efficiently utilize multi-source medical information to achieve precise diagnosis and intelligent decision-making has become a core direction in the development of medical artificial intelligence (AI). Although traditional unimodal algorithms (e.g., models based solely on CT, MRI, or ultrasound images) have achieved certain results in specific tasks, their inability to model semantic correlations among imaging, text, and laboratory data often leads to insufficient stability and limited interpretability of diagnostic outcomes, making it difficult to meet the comprehensive decision-making needs of complex clinical scenarios.

In recent years, multimodal large models have demonstrated remarkable cross-modal understanding and knowledge transfer capabilities in natural image processing and general vision-language tasks, providing a new technical paradigm for medical AI. However, the direct application of such models in medical scenarios still faces multiple challenges: First, there are significant differences between the medical semantic system and general language models, making it difficult to accurately characterize disease features and imaging details. Second, complex lesion morphology and uneven sample distribution in medical data increase the difficulty of model generalization. Third, clinical data involves privacy-sensitive information, making data security and ethical compliance prerequisites for research.

Research on medical multimodal large models aims to comprehensively utilize multi-source heterogeneous data, including medical imaging (e.g., CT, MRI, X-ray), EMRs, and laboratory reports, to establish a unified semantic representation and reasoning mechanism, enabling end-to-end intelligent analysis covering disease identification, lesion localization, report generation, and disease prognosis prediction. This research direction not only helps improve the efficiency and accuracy of clinical diagnosis but also provides clinicians with interpretable and traceable auxiliary decision support, boasting broad clinical application prospects.

Based on the hospital's abundant clinical data resources and the research team's algorithm development foundation, this study intends to construct a multimodal large model system for medical imaging diagnosis, realizing a closed-loop intelligent analysis process from multimodal information fusion to diagnostic report generation.

During the research implementation, strict adherence to medical ethical standards will be maintained to fully protect patients' right to informed consent, privacy, and data security. To ensure the scientificity and compliance of the research design, this project must pass ethical review prior to official launch, in accordance with relevant regulations such as the Declaration of Helsinki, International Ethical Guidelines for Biomedical Research Involving Human Subjects, and Ethical Review Measures for Life Science and Medical Research Involving Humans, thus ensuring the organic unity of scientific research and ethical principles and laying a compliant foundation for subsequent clinical validation and application promotion.

## 2. Research Objectives

This study aims to construct a multimodal medical large model centered on medical imaging, integrating textual reports and structured laboratory data, to achieve unified modeling of multiple tasks including disease diagnosis, lesion segmentation and localization, report generation, and pathological correlation analysis. Through deep learning and validation on real-world clinical data,

this study seeks to connect the entire workflow from data collection and model construction to intelligent diagnosis, promoting the clinical translation and trustworthy application of AI in medical diagnosis.

To achieve this objective, the study plans to conduct exploration and research in the following three aspects:

### **Construction of a multimodal data fusion and semantic alignment**

By integrating multi-source heterogeneous data such as imaging, text, and laboratory tests, a unified feature representation space will be established to realize cross-modal semantic alignment and correlation modeling. A multimodal model capable of simultaneously performing tasks including disease classification, lesion segmentation and localization, and imaging report generation will be designed, achieving a comprehensive upgrade of medical imaging intelligent analysis from "recognition" to "interpretation" and supporting the comprehensive diagnosis of multiple diseases.

### **Construction and pre-training of multimodal large models**

Based on clinical multimodal data, a large model architecture with unified perception and generation capabilities will be designed, and research on pre-training and instruction tuning will be carried out to equip the model with general transfer capabilities for tasks ranging from disease identification and lesion analysis to report generation.

### **Validation of model generalization performance**

The generalization performance of the model in multi-disease and multimodal scenarios will be verified to provide interpretable decision-making basis for clinical auxiliary diagnosis.

Through the above research, it is intended to construct a foundational medical multimodal model with general understanding, diagnostic capabilities, and generalization ability, expecting to promote the intelligent application of medical data, improve the efficiency and accuracy of disease diagnosis, and provide clinicians with a trustworthy intelligent diagnostic auxiliary system.

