## **3. Research Design and Methods**

### **Prospective Validation of a Multimodal Imaging Large Model**

#### **(I) Study Design Type and Methodology**

This study is a single-center prospective observational study, aiming to conduct prospective validation and optimization of the established medical multimodal large model based on real-time collected clinical multimodal data (imaging, medical records, laboratory tests, reports, etc.). No additional interventions will be imposed on patients' diagnosis and treatment processes during the study; relevant data will only be collected synchronously during routine clinical examinations and diagnostic procedures, making it a non-interventional, minimal-risk prospective study.

During the study period, all newly diagnosed cases meeting the inclusion criteria will be consecutively enrolled. The research team will conduct prospective inference and performance validation of the multimodal medical large model based on imaging findings, EMR text, and laboratory test data, systematically evaluating the model's performance in tasks such as disease diagnosis, lesion localization, and report generation. Study results will be compared with clinicians' actual diagnostic conclusions and pathological gold standards to verify the model's generalization ability and clinical applicability in real-world scenarios.

The overall study protocol includes the following phases:

1. **Case recruitment and data collection:** Patients undergoing imaging examinations in the hospital will be consecutively recruited according to pre-defined inclusion criteria. Study data are derived from routine clinical workflows, covering imaging data, EMRs, laboratory results, and radiology reports. All data will undergo de-identification and quality control before being entered into the study database, with only the minimum necessary information retained.

2. **Model application and inference:** The research team will deploy the multimodal model in the hospital's secure computing environment. For each enrolled patient, the model will automatically generate disease predictions, lesion localization results, and diagnostic reports based on their imaging data and corresponding clinical text.

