## **(III) Patient Inclusion, Exclusion, and Withdrawal Criteria**

### **Inclusion Criteria**

1. Adult patients aged  $\geq 18$  years;
2. Undergoing imaging examinations (CT, MRI, ultrasound, etc.) in the hospital during the study period;
3. Examination items corresponding to the disease types or systems focused on by the study (hepatobiliary and pancreatic system);
4. Possessing at least complete imaging data and radiology diagnostic reports, with relevant medical record information as supplementary modalities;
5. Patients or their legal representatives signing an informed consent form, agreeing to the use of their de-identified data for scientific research model validation;
6. Case data passing quality review, with good imaging quality and standardized text records.

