#### **(IV) Detailed Research Protocol**

##### **Research Data Sources**

Data for this study are derived from patients undergoing routine clinical examinations in the hospital during the study period. Data collection is accomplished relying on the hospital's existing information systems, without imposing additional burdens on patients or interfering with diagnosis and treatment processes. All data are real-world multimodal information generated in routine clinical practice, mainly including:

- Medical imaging data from the Department of Radiology, covering original images and reconstructed sequences such as CT, MRI, and ultrasound, as well as manual annotations, masks, or structured descriptions, which serve as reference standards for model validation;
- Radiology diagnostic reports, including examination findings, diagnostic conclusions, and physician recommendations. All images undergo unified format conversion (e.g., DICOM to NIfTI) and quality assessment before being imported into the study database, with sequences containing artifacts or defects excluded;
- Text data from the electronic medical record system, including admission records, discharge summaries, progress notes, and surgical records. Prior to import, text data undergo automated de-identification to remove sensitive information such as names, hospital admission numbers, ID card numbers, and contact information, retaining only key clinical course points relevant to the research objectives;
- Structured laboratory data from the laboratory information system, including quantitative data such as complete blood count, biochemical indicators, tumor markers, and coagulation function, which are aligned with imaging examinations via timestamps to support cross-modal feature fusion and quantitative analysis of disease states in the model.

All research data undergo rigorous de-identification before being imported into the analysis environment, with only the minimum necessary information required for the study retained. Data collection and usage comply with the Personal Information Protection Law, Data Security Law, and the hospital's ethical requirements. All patients sign a written informed consent form prior to enrollment, explicitly agreeing to the use of their de-identified data for scientific research model validation and performance optimization. The entire research process is conducted under the approval and supervision of the IRB.

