## **4. Sample Size Calculation**

This study encompasses multiple stages including retrospective model development and prospective clinical validation. Each stage has distinct objectives, leading to differences in the basis and methods of sample size estimation. This section elaborates on the basis, parameter sources, and methods for sample size calculation in each part, and clearly presents the key calculation formulas.

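### The protocol promises verified generalization, but one hospital and one organ system can show only local stability, and development patients are not kept out of the validation set

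*Protocol*

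**What the plan says.** Section 2 (Validation of model generalization performance) sets the objective: "The generalization performance of the model in multi-disease and multimodal scenarios will be verified". It goes on to say that the work is meant to "construct a foundational medical multimodal model with general understanding, diagnostic capabilities, and generalization ability". Section 3(I) says the comparison with clinicians and pathology serves "to verify the model's generalization ability and clinical applicability in real-world scenarios". Sample Size Estimation Process, repeated in section 4 (Prospective Study Phase), adds that about 2000 patients are enough to evaluate generalization accurately.

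The design is narrower:

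- **Site.** "This study is a single-center prospective observational study" (section 3(I)). Research Data Sources confirms it: "Data for this study are derived from patients undergoing routine clinical examinations in the hospital during the study period".
- **Scope.** Inclusion criterion 3 reads "Examination items corresponding to the disease types or systems focused on by the study (hepatobiliary and pancreatic system".
- **Origin of the model.** Section 1 introduces its construction with "Based on the hospital's abundant clinical data resources and the research team's algorithm development foundation". Section 4 says "This study encompasses multiple stages including retrospective model development and prospective clinical validation", and its Retrospective Study Phase puts the fine-tuning set at 10,000–20,000 image-text pairs without naming their source.
- **Meaning of generalization.** Secondary Outcome Indicators defines it as stability across devices, disease types and populations. Statistical Analysis Procedures plans stratified analyses on that basis.

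**The concern.** Two things are at stake.

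The first is what the study may conclude. Strata within one hospital show whether performance holds up across local subgroups. They say nothing about another hospital's equipment, reporting habits or case mix, or about other organ systems. A report that generalization was verified would claim more than the data can carry.

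The second is whether validation patients are new to the model. If some contributed scans or reports to development, the model may do better on them than on unseen patients. Diagnosis, segmentation and report-similarity scores could all be affected. The error would probably run in the model's favor, in a study sized around a 5-point advantage over manual diagnosis.

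**Working it through.** **Figures near the claim.** The generalization claim itself carries no figure. The adjacent one is 500–600 cases per group for 85% against 80% accuracy at alpha 0.05 and 80% power. A standard two-sided comparison of two proportions gives 906 per group, so that figure does not reproduce. This is a separate matter, and nothing below depends on it.

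**Step 1: what 2000 patients buy.** At 85% accuracy, the 95% half-width is 1.96 × √(0.85 × 0.15 / 2000) = 0.0156, about 1.6 points. That precision applies to this hospital's eligible patients. Between-hospital variation cannot be estimated from one hospital at any sample size.

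**Step 2: claim against design.**

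| Dimension | Claim | What the design observes |
|---|---|---|
| Hospitals | general, real-world | 1; no external site or dataset is mentioned |
| Organ systems | foundational, general diagnostic ability | hepatobiliary and pancreatic only |
| Devices, diseases, populations | stability | testable, within that hospital and organ system |

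Only the last row is supported.

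**Step 3: are development patients kept out?** Taking the places that could do it in turn:

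- The inclusion criteria ask for adults imaged during the study period, in this organ system, with consent and adequate data. None concerns earlier use of the patient's data.
- The five exclusion criteria cover refusal, unusable images, missing or unmatched clinical data, special pathology or altered anatomy, and privacy or legal risk. None covers development use.
- The four withdrawal criteria do not add it.
- Section 3(I) describes the enrolled cases as newly diagnosed. This is a partial guard. It does not appear in the inclusion criteria, and the first phase in the same section recruits patients undergoing imaging generally. A new diagnosis also does not rule out earlier imaging at the hospital.
- Research Data Sources strips admission and ID card numbers from record text before import and de-identifies all data before analysis. No matching against the development set is planned before that.

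**Step 4: the second route.** The fourth phase in section 3(I) has new cases feed continued fine-tuning as well as validation. It does not say that a case is scored before it is used for tuning, or by a version not tuned on that patient. Excluding earlier development patients alone would leave this route open.

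**Step 5: size of any bias.** Inflation in accuracy = share of overlapping patients × gain in those patients. The document gives neither input. Purely as an assumption, a 5% share with a 5-point gain gives 0.05 × 5 = 0.25 points, and a 30% share with a 15-point gain gives 0.30 × 15 = 4.5 points. The ends differ 18-fold (4.5 / 0.25), so this shows what would have to be known and is not an estimate.

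**The case against.** The strongest reply is that the protocol uses its own meaning of generalization. The objective speaks of multiple diseases and modalities, the secondary outcome names devices, disease types and populations, and all of these can be compared inside one hospital. The single center and the organ system are openly declared, no section says another hospital will be tested, and the foundational-model sentence states an intention and is not an endpoint. This stands in part. The narrow meaning is testable and should be kept. But the objective, the design section and both sample-size passages use the term without that limit, next to a stated aim of general diagnostic ability.

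Four stronger readings are tempting and are not supported:

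- *A patient with a long-known lesion in the development set is plainly eligible.* The criteria allow it, but the newly diagnosed wording in section 3(I), if applied, would not. The two must be reconciled.
- *Overlap could never be traced later.* Identifiers are removed before import. A linkage key is neither described nor ruled out, and consent withdrawal during the study suggests some link back to the patient.
- *Scanners, radiologists and reporting style are shared between development and validation.* Section 1 points to the same hospital, but section 4 does not name the source of the fine-tuning pairs, and the base model was pre-trained beforehand. Same-hospital development is the reasonable reading, not a stated fact.
- *Accuracy will be inflated by up to 4.5 points.* That rests wholly on assumed inputs and makes no allowance for the newly diagnosed restriction.

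**Conclusion.** The point holds in a limited form. The design can show within-hospital stability in hepatobiliary and pancreatic imaging. It cannot verify generalization to other hospitals (0 tested) or other organ systems (0 tested). This part rests on the stated site and scope alone and needs no assumption.

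Separately, nothing reliably keeps development patients out of the validation set, and the planned fine-tuning on new cases opens a second route. Concern about the first route is greatest if development used this hospital's records, as section 1 indicates. The likely direction is in the model's favor. The amount of overlap, and so the size of the bias, cannot be derived from the document. The study can still be run, but its stated conclusion needs narrowing and its validation set needs protecting.

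**What to change.** 1. **Separate the patients.** Add an exclusion criterion removing from the validation set any patient whose data were used in model development or tuning. Match on a hashed hospital identifier before de-identification, and report the number removed.
2. **Reconcile eligibility.** Make the newly diagnosed wording in section 3(I) agree with the inclusion criteria and with the recruitment phase.
3. **Apply the same rule to continued fine-tuning.** State that each case is scored by a model version not tuned on that patient.
4. **Narrow the claim.** In section 2, section 3(I) and both sample-size passages, describe the study as prospective validation in hepatobiliary and pancreatic imaging at one hospital, with stability assessed across local devices, disease types and populations. State that transfer to other hospitals or organ systems is not tested.

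The cost is one record-matching step, version tracking for the model, some repeat patients lost, and a more modest conclusion. The matching is easiest to arrange before the scheduled start on November 15, 2026, while identifiers are still attached.

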## **3. Research Design and Methods**

### **Prospective Validation of a Multimodal Imaging Large Model**

#### **(I) Study Design Type and Methodology**

This study is a single-center prospective observational study, aiming to conduct prospective validation and optimization of the established medical multimodal large model based on real-time collected clinical multimodal data (imaging, medical records, laboratory tests, reports, etc.). No additional interventions will be imposed on patients' diagnosis and treatment processes during the study; relevant data will only be collected synchronously during routine clinical examinations and diagnostic procedures, making it a non-interventional, minimal-risk prospective study.

During the study period, all newly diagnosed cases meeting the inclusion criteria will be consecutively enrolled. The research team will conduct prospective inference and performance validation of the multimodal medical large model based on imaging findings, EMR text, and laboratory test data, systematically evaluating the model's performance in tasks such as disease diagnosis, lesion localization, and report generation. Study results will be compared with clinicians' actual diagnostic conclusions and pathological gold standards to verify the model's generalization ability and clinical applicability in real-world scenarios.

The overall study protocol includes the following phases:

1. **Case recruitment and data collection:** Patients undergoing imaging examinations in the hospital will be consecutively recruited according to pre-defined inclusion criteria. Study data are derived from routine clinical workflows, covering imaging data, EMRs, laboratory results, and radiology reports. All data will undergo de-identification and quality control before being entered into the study database, with only the minimum necessary information retained.

2. **Model application and inference:** The research team will deploy the multimodal model in the hospital's secure computing environment. For each enrolled patient, the model will automatically generate disease predictions, lesion localization results, and diagnostic reports based on their imaging data and corresponding clinical text.

3. **Clinical comparison and result documentation:** The model outputs will be subject to double-blind evaluation by radiologists and clinicians from relevant departments, compared with the final pathological or clinically confirmed results, and the accuracy, consistency, and interpretability of model predictions will be documented.

4. **Model iteration and continuous validation:** On the premise of ensuring ethical and privacy compliance, the research team will use newly collected data for continuous model fine-tuning and validation, analyzing its stability and robustness across different disease types, devices, and operational conditions.

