##### **Primary Outcome Indicators**

1. Disease diagnosis task: Area Under the Curve (AUC), Sensitivity, Specificity, Accuracy, F1-score;
2. Lesion localization and segmentation task: Dice coefficient, Hausdorff distance;
3. Report generation task: BLEU, ROUGE, CIDEr, etc.

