#### **Statistical Analysis Procedures**

This study adopts intention-to-treat (ITT) analysis as the primary analytical strategy, conducting systematic statistical analysis on data from all enrolled cases. First, descriptive statistics are performed to summarize the baseline characteristics of patients, including age, gender, disease type, and imaging equipment source. Continuous variables are presented as mean  $\pm$  standard deviation or median depending on their distribution type, while categorical variables are expressed as frequencies. Inter-group differences are analyzed using appropriate statistical methods based on data characteristics: the t-test is used for normally distributed data, and the Mann–Whitney U test is used for non-normally distributed data.

In the analysis of primary outcome indicators, this study focuses on evaluating the model's performance in three core tasks: disease diagnosis, lesion localization, and report generation. For the disease diagnosis task, clinical final diagnosis or pathological results are used as the gold standard to calculate AUC, Sensitivity, Specificity, Accuracy, and F1-score, and receiver operating characteristic (ROC) curves are plotted to comprehensively assess the model's classification ability. For the lesion localization and segmentation task, expert annotations are used as references to calculate the Dice coefficient and Hausdorff distance, measuring the model's performance in lesion recognition range and boundary precision. For the report generation task, model-generated reports are compared with radiologists' reports at the text level, and natural language generation metrics such as BLEU, ROUGE, and CIDEr are used to evaluate language quality and semantic consistency.

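### The Protocol gives two enrolment rules; the one limited to newly diagnosed cases, taken literally, leaves no disease-free patients for a disease-versus-no-disease specificity or AUC

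*Protocol*

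**What the plan says.** Who is enrolled is described in three places in the Protocol.

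- Section 3 (I), second paragraph: "During the study period, all newly diagnosed cases meeting the inclusion criteria will be consecutively enrolled".
- Section 3 (I), phase 1 of the study outline: "Patients undergoing imaging examinations in the hospital will be consecutively recruited according to pre-defined inclusion criteria".
- Section 3 (III), Inclusion Criteria, item 2: "Undergoing imaging examinations (CT, MRI, ultrasound, etc.) in the hospital during the study period". Item 3 limits this to examinations of the hepatobiliary and pancreatic system. The other items concern adult age, complete images and report, consent, and data quality. None of the six asks for a diagnosis.

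The primary indicators for the diagnostic task are "Area Under the Curve (AUC), Sensitivity, Specificity, Accuracy, F1-score" (section 3 (IV), Primary Outcome Indicators). Under Statistical Analysis Procedures, "clinical final diagnosis or pathological results are used as the gold standard to calculate AUC, Sensitivity, Specificity, Accuracy, and F1-score". The objectives describe more than one disease: "The generalization performance of the model in multi-disease and multimodal scenarios will be verified" (section 2). None of these places names the target condition(s), or says which patients count as negative for specificity and AUC.

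**The concern.** The first statement makes an established new diagnosis a condition of entry. The other two make an eligible examination the condition, whatever it shows. Specificity and AUC both need patients who are negative on the reference standard, and the choice of rule decides whether disease-free patients are in the cohort at all.

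If recruiting staff follow the first statement, the study cannot show how often the model reports disease in patients who have none. A model that over-calls would then look good on a primary outcome, and the claim to real-world performance would lose much of its basis. The accuracy comparison that drives the sample size (85% for the model against 80% for manual diagnosis) would also refer to a different case mix under each rule. Analysis cannot repair this later, because disease-free patients who were never recruited cannot be added. Who is enrolled is a matter for the protocol, not for a statistical analysis plan.

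**Working it through.** **The Protocol's own figures.** It gives no prevalence, no expected specificity and no expected number of negatives, so there is no stated figure on this point to reproduce. The sample-size calculation concerns accuracy and does not bear on this conflict.

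**Inputs.** N = 2000 patients (Sample Size Estimation Process), all taken as evaluable. Assumed: specificity 0.85; disease prevalence 30–60%. Neither assumption comes from the Protocol, whose 85% is an accuracy.

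**Step 1: do the statements agree?**

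| Place | Examination required | Diagnosis required |
|---|---|---|
| 3 (I), second paragraph | yes, through the inclusion criteria | yes, newly diagnosed |
| 3 (I), phase 1 | yes | no |
| 3 (III), items 1–6 | yes, hepatobiliary or pancreatic | no |

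The reference to the inclusion criteria in the first row does not remove the added condition. It makes the cohort the intersection: newly diagnosed and also eligible.

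**Step 2: literal cases-only cohort, contrast disease versus no disease.** Negatives = 0. Specificity = true negatives / 0, which is undefined. AUC compares diseased with disease-free patients in pairs; the number of pairs is 2000 × 0 = 0, so it is undefined too. With prevalence π, accuracy = π × sensitivity + (1 − π) × specificity, and at π = 1 this is sensitivity alone. A model that always calls disease has sensitivity 1 and specificity 0, so its accuracy equals π: 100% in the cases-only cohort, but 30–60% at the assumed prevalences.

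**Step 3: cohort under the inclusion criteria, same contrast.** Negatives = 2000 × (1 − π), and the 95% half-width is 1.96 × √(0.85 × 0.15 / negatives).

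- π = 60%: 800 negatives; 1.96 × √(0.1275 / 800) = 0.025.
- π = 30%: 1400 negatives; 1.96 × √(0.1275 / 1400) = 0.019.

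**Step 4: several diseases, one-versus-rest.** Here patients with another disease count as negatives for the target disease, so negatives can exist even if everyone is diseased. The same formula over assumed non-target shares of the 2000 gives:

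| Non-target share | Non-target patients | 95% half-width (points) |
|---|---|---|
| 0% | 0 | not estimable |
| 5% | 100 | 7.0 |
| 10% | 200 | 4.9 |
| 25% | 500 | 3.1 |
| 50% | 1000 | 2.2 |
| 75% | 1500 | 1.8 |

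One-versus-rest specificity and AUC are therefore estimable in a cases-only cohort. They measure confusion between diseases. They say nothing about false alarms in disease-free patients.

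**The case against.** The strongest reply is that the cases-only cohort is a product of loose wording. The Protocol often uses the word case for any enrolled patient, for example in the sample-size and analysis sections. The sentence itself refers to the inclusion criteria, and those criteria, the recruitment phase and the data-source section all describe patients having routine examinations. On this view the operative criteria already give the right population.

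Much of that stands as a guess at intent. It does not dispose of the point, because loose use of case does not explain the word diagnosed, and the sentence states who will be enrolled.

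Three stronger readings may tempt a reader, and the document supports none of them.

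- *That specificity and AUC cannot be estimated in this study.* This needs both the literal sentence and a disease-versus-no-disease contrast. The Protocol fixes neither: the model is multi-disease, and one-versus-rest measures would remain available.
- *That the model would run on patients whose answer is already on file.* The Protocol describes real-time collection and prospective inference, and no passage says that the diagnosis is recorded before the model runs.
- *That the inclusion criteria admit everyone who is imaged.* They are limited to hepatobiliary or pancreatic examinations in consenting adults with adequate data, and exclusions follow.

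**Conclusion.** The conflict is real and should be resolved before enrolment, which is scheduled to start on November 15, 2026. Section 3 (I) contains a stated rule that, if followed, selects on the outcome. Its cost is then total for one estimand: 0 disease-free patients of 2000, against 800–1400 under the inclusion criteria. Between-disease measures would survive, but over-calling in disease-free patients would go unmeasured, and accuracy would refer to a different case mix.

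The conclusion is conditional. The loss follows only from the literal sentence combined with a disease-versus-no-disease contrast, and the Protocol settles neither. The counts of negatives rest on an assumed prevalence of 30–60%, and the half-widths also on an assumed specificity of 85%. The inconsistency itself, and the missing definition of the negative class, rest on no assumption.

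**What to change.** 1. In the second paragraph of section 3 (I), replace the reference to newly diagnosed cases so that the sentence enrols all consecutive patients who meet the inclusion criteria, regardless of the eventual diagnosis. It then agrees with phase 1 and section 3 (III).
2. Beside the primary diagnostic indicators, name the target condition(s) and the negative class for specificity and AUC: disease-free patients, patients with other diseases, or both reported separately.
3. Reconcile this with Exclusion Criteria item 4. Its exclusion of unusual pathology may depend on the final diagnosis, and withdrawal criterion 1 allows removal on that ground after enrolment. If such exclusions stay, say what information they are decided on.

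Cost: a few sentences in three places and no additional patients. The real downside is for the segmentation task. At an assumed prevalence of 30–60%, 2000 × 0.30 = 600 to 2000 × 0.60 = 1200 diseased patients would contribute, which is 40–70% fewer than in a cases-only cohort of 2000. The sponsor should check that this number is enough for the Dice and Hausdorff results.
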